4.2 Study Outcome Measures

4.2.1 Primary Outcome Measures

Each subject will have 12-months of follow-up. All outcomes will be assessed at 2-month intervals.

Our primary outcome measure is depressive symptomatology, as measured by the QIDS – and operationalized as an incident rate of moderate to severe episodes over time and as symptom trajectories.

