12.1 Study Hypotheses

Given PSE's penetrance and acceptability in prior studies [21-23], we hypothesize that its uptake will exceed 85% among women in this comparator; that it will provide sustained symptom relief; and that it will prevent the need for referring certain mothers (i.e. those with subsyndromal depression) to more formal care. By virtue of improved coping skills and behavioral activation, we hypothesize that PSE will make referrals to formal care more effective (for those who need it) than Engagement Interviewing alone. However, it is also important to assess the possibility that PSE may represent an unnecessary step that only serves to delay more definitive care and symptom relief. Our ultimate goal is to reduce disparities in access to mental health care for low-income mothers; and to improve outcomes for them and their children.

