12.2 Sample Size Determination

Sample Size. For this project, our results would be used to build a case for intervention implementation within the PCMH. Because small differences in outcomes would fail to make this case effectively, we aim to detect a 33% relative reduction in symptomatic depressive episodes (defined as a bimonthly QIDS score ≥ 11) – which is both clinically important and consistent with previous work. All estimates assume 80% power and a two-sided alpha of 0.05.

1. **Incident rate of moderate to severe symptomatic episodes.** Using Poisson regression analysis, with 100 analyzable subjects in each study group and a Poisson rate of 1.2 symptomatic episodes per 6 follow-up assessments in one group (gleaned from data among a demographically similar population of peripartum women), we can detect a 33% reduction in the rate of episodes to 0.8 in the other group.
2. **Depressive symptoms over time.** In prior longitudinal data, we have observed the following mean QIDS scores for each follow-up month and assume these values for one group in the planned study: 8.2; 7.6; 7.5; 6.9; 7.2 (common SD, 5.9). We hypothesize that the following mean QIDS scores in the other group would be achievable and clinically significant: 7.2; 6.6; 5.5; 4.4; 4.2, resulting in a mean difference of 3 points at the final study time point in QIDS scores across study groups (note: a 3-point difference in QIDS scores, in the majority of cases, would move a subject across a clinical cutoff corresponding to mild, moderate or severe symptoms). Using a two-group repeated measures design analyzed by generalized estimating equations or mixed linear models, noting within-subject correlations of 0.7 for values separated in time by one month and 0.6 for those separated for two months or more in our longitudinal analysis, we can detect the above differences in the means between groups over time with 100 subjects per study group with 89% power for a correlation of 0.7 and 77% for correlation of 0.6.
3. **HTE analysis.** If we assume that equal numbers of women will be recruited pre- and postnatally, 100 subjects per arm will provide 86% power to detect differential effects of treatment between pregnant and postpartum women as extreme as a rate ratio of 0.38 in the prenatal stratum (rate in one group=0.45 vs. rate in the other=1.2) compared to a rate ratio of 0.96 in the postpartum stratum (rate in one group=1.15 vs. rate in the other=1.2).

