Therefore, with an analyzable sample of 100 subjects per study group, we will be able to detect with adequate statistical power differences in incident rates of elevated QIDS scores and mean QIDS scores over time that are of clear clinical relevance. Based on our current data, we estimate that 20% of mothers with positive EPDS screens will refuse participation; 77% will meet full eligibility criteria; and we will experience a 15% attrition rate over the course of the study. Therefore, to ensure that we assess outcomes in 200 study subjects, we will approach 374 mothers with depressive symptoms and randomize 230. This sample size will be readily available from our two clinic sites.

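### QIDS trajectory power: the printed 89% does not fit 2-monthly visits, and the follow-up-only test behind both printed figures depends on an unstated sixth mean and an unstated role for baseline

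*Combined protocol and SAP*

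**What the plan says.** Section 4.2.1 defines the primary outcome as depressive symptoms on the QIDS, "operationalized as an incident rate of moderate to severe episodes over time and as symptom trajectories", and adds: "All outcomes will be assessed at 2-month intervals". Section 9 (Follow-Up Procedures) confirms a 2-monthly schedule for 12 months, which makes six follow-ups, each with a 6-week window. Item 1 of Section 12.2 also counts six.

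Section 12.2 opens its calculations with "All estimates assume 80% power and a two-sided alpha of 0.05". Item 2 lists five mean QIDS scores per group with a common SD of 5.9, ending in "a mean difference of 3 points at the final study time point". It describes the correlations as "noting within-subject correlations of 0.7 for values separated in time by one month and 0.6 for those separated for two months or more", and states power "with 100 subjects per study group with 89% power for a correlation of 0.7 and 77% for correlation of 0.6". It does not say which of the two applies. The section concludes that 100 analysable women per group can detect, "with adequate statistical power differences in incident rates of elevated QIDS scores and mean QIDS scores over time", effects of clinical relevance.

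Section 12.3 plans GEE or a mixed linear model for group-by-time effects. It gives neither the coding of time nor the role of baseline QIDS. Section 12.1 expects of PSE that "it will provide sustained symptom relief".

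**The concern.** There are two linked problems. First, the higher power figure uses a correlation that the plan itself reserves for values one month apart, and the schedule has no such nominal pair. A reader who takes 89% as the power, or who takes the 80% statement to cover item 2, is relying on a figure that the design does not have.

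Second, the two printed figures match a test on follow-up visits alone. Such a test responds only to change in the gap between arms during follow-up. If PSE produced most of its benefit by the first assessment and then held it, the test would have little to detect, although Section 12.1 hopes for lasting relief. A model with baseline as a time point behaves very differently. Section 12.3 allows either, so an analysis of the primary outcome could be settled after the data are seen.

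**Working it through.** **Inputs (Section 12.2 item 2).** Group 1 means 8.2, 7.6, 7.5, 6.9, 7.2; group 2 means 7.2, 6.6, 5.5, 4.4, 4.2; differences 1, 1, 2, 2.5, 3. SD 5.9 (variance 34.81), n = 100 per arm, two-sided alpha 0.05.

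**1. Reproduce the plan.** Take a group-by-time test with visit as a category, five follow-ups, no baseline and equal correlation ρ at every gap.

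- Noncentrality λ = n × SS / (2 × SD² × (1 − ρ)), where SS is the sum of squares of the differences about their mean.
- Mean difference = 9.5/5 = 1.9; SS = 0.81 + 0.81 + 0.01 + 0.36 + 1.21 = 3.2.
- ρ = 0.7: λ = 320/(2 × 34.81 × 0.3) = 15.32. F with 4 and 195 df gives 89.0% (printed: 89%).
- ρ = 0.6: λ = 320/(2 × 34.81 × 0.4) = 11.49, giving 77.1% (printed: 77%).

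The arithmetic is right. A 1-df linear trend does not reproduce the pair: at 0.6, λ = 10.86 and power is 91%.

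**2. Which correlation applies.** All nominal visits are at least two months apart, so the plan's own rule selects 0.6. The 89% needs 0.7 at every gap. Wide windows could bring some visits closer together. Setting pairs 1-2 and 3-4 to 0.7 and the rest to 0.6 gives λ = 10.26 and 72%; pairs 2-3 and 4-5 give λ = 10.94 and 75%. These are examples, not bounds.

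**3. Six follow-ups at 0.6 (5 and 194 df).** A sixth difference e makes SS = 3.2 + (5/6)(e − 1.9)². The plan gives no e, so these values are assumptions.

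| Sixth difference | SS | λ | Power |
|---|---|---|---|
| 1.0 | 3.875 | 13.92 | 82% |
| 1.9 | 3.200 | 11.49 | 73% |
| 2.5 | 3.500 | 12.57 | 78% |
| 3.0 | 4.208 | 15.11 | 86% |

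**4. Shape of the gap, same test without baseline, six visits at 0.6 (assumed patterns).**

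| Gaps | SS | λ | Power |
|---|---|---|---|
| 1,2,3,3,3,3 | 3.500 | 12.57 | 78% |
| 1,3,3,3,3,3 | 3.333 | 11.97 | 75% |
| 2,3,3,3,3,3 | 0.833 | 2.99 | 22% |
| 3,3,3,3,3,3 | 0 | 0 | 5% |

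**5. Baseline as a time point, arms constrained equal there, visit as a category.** This is a joint test of the k follow-up differences given baseline. Baseline SD 5.9 and baseline-to-follow-up correlation r of 0.3 to 0.6 are assumptions. With c = 0.6 − r²,

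λ = (n/2) × [Σd² − c(Σd)²/(0.4 + kc)] / (0.4 × SD²), F with k and 198 − k df.

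- Plan's five differences (Σd² = 21.25, Σd = 9.5): r = 0.3, λ = 20.28, 95%; r = 0.6, λ = 27.69, 99%.
- With a sixth difference of 1.0, 1.9 or 3.0: 95.0%, 93.8%, 98.0% at r = 0.3; 98.8%, 98.9%, 99.8% at r = 0.6.
- Constant 3 points over six visits: r = 0.3, λ = 22.42, 96%; r = 0.6, λ = 42.15, over 99%.

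With linear time instead of categories, the constant 3-point pattern at r = 0.3 falls to 77%.

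**The case against.** The plan prints 77% next to 89% and labels each with its correlation, so nothing is hidden, and about 107 analysable women per arm would give 80%. That stands: taken alone, the 89% is a wording correction.

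A reader might infer that the trial is underpowered and needs more participants. The documents do not support this. On the same five means at 0.6, a linear trend has 91%, and the constrained model has 95% or more under the stated assumptions. The 77% belongs to one unstated choice of test.

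A reader might also infer from the 5% that the trial cannot see a sustained benefit. That goes too far, for three reasons.

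- The 5% needs an exactly flat gap. Item 2 assumes a gap growing from 1 to 3 points, and a full PSE course is six weekly or biweekly sessions (Section 5), so some women may still be in treatment at the first follow-up. If the gap starts at 1 point and then rises quickly to 3, power is 75% to 78%.
- The exclusion of baseline is inferred from the match to the two printed figures. Section 12.3 would equally permit a model that includes baseline.
- The episode-rate form of the primary outcome would still respond to a flat gap.

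What remains is that power falls steeply as the gap flattens (22% for 2,3,3,3,3,3) and that the text does not exclude the weaker test.

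Finally, other pre-specified models are defensible. The essential step is to choose one in advance; the model below is a recommendation.

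**Conclusion.** The point holds in this limited form. On a 2-monthly schedule the plan's own correlation is 0.6, so the 89% should go. The matching follow-up-only test has 77% for five means, below the stated 80%. Its six-visit power is 73% to 86% for an assumed sixth difference of 1 to 3 points, and stays open until a sixth mean is given. If baseline is left out, power depends strongly on when the gap opens.

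The first part rests only on figures in the plan. The results for the sixth visit, the gap patterns and the constrained model rest on labelled assumptions; at a baseline correlation of 0 the 94% floor would be about 92%. This should be corrected before data are seen. It is not evidence of an arithmetic error or of an inadequate sample size.

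**What to change.** 1. **Section 12.2.** Delete the 89%, name 0.6 as the planning correlation, list six means per group, and state the power for the model that will be used. If the follow-up-only test is kept, state 77% for the five listed means and exempt item 2 from the 80% statement.
2. **Section 12.3.** Pre-specify the trajectory analysis with baseline QIDS as a time point, arms constrained equal at baseline, and visit as a category. This also makes the missing sixth mean matter much less.
3. **Optional.** Report the baseline-adjusted 12-month difference, which is the plan's own 3-point target, as a supporting contrast that carries no separate claim of success.

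Items 2 and 3 need the QIDS to be among the depression scales of the baseline survey described in the synopsis. The schedule of events is not available to confirm this. If it is, the cost is SAP wording only, with no new data or visits. The downside is a model form fixed in advance. Power also stays limited for smaller effects: a constant 2 points gives about 62% to 91% in the constrained model at the same assumed baseline correlations.

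### Randomizing 230 women with 15% attrition leaves about 195 with outcomes, not the 200 that section 12.2 promises

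*Combined protocol and SAP*

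**What the plan says.** Section 12.2 (Sample Size Determination) builds its calculations on 100 women per arm. The Poisson item is stated "with 100 analyzable subjects in each study group and a Poisson rate of 1.2 symptomatic episodes per 6 follow-up assessments in one group", and concludes that "we can detect a 33% reduction in the rate of episodes to 0.8 in the other group". A general statement covers the section: "All estimates assume 80% power and a two-sided alpha of 0.05". The trajectory item gives 89% or 77% power, depending on the within-subject correlation, and the heterogeneity item gives 86%, both again for 100 per arm.

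The closing paragraph of the section moves from analyzable to randomized women. It assumes 20% refusal and 77% eligibility, and continues: "we will experience a 15% attrition rate over the course of the study. Therefore, to ensure that we assess outcomes in 200 study subjects". The numbers it then sets are 374 women approached and 230 randomized. The figure of 230 is repeated in the synopsis and in section 5 (Study Design). No inflation formula is given, and nothing elsewhere changes the 15% or the 200.

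**The concern.** The closing paragraph presents 200 as what remains of 230 after 15% are lost. Taking 15% from 230 leaves fewer than 200, so the stated inputs and the stated result cannot both stand.

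The 100 per arm is the base for all three calculations in section 12.2 and for its conclusion that power is adequate. The Poisson calculation, which serves the primary outcome, has almost no slack at 100 per arm, so even a small shortfall could take it just under 80%. Section 12.3 commits to CONSORT reporting, so readers will set the planned analyzable number beside the number achieved.

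**Working it through.** **Inputs, all from section 12.2 unless noted.** Target 200 analyzable (100 per arm); 230 randomized, 1:1 (section 5), so 115 per arm; attrition 15%; refusal 20%; eligibility 77%; 374 approached. Two-sided alpha 0.05. Poisson rates 1.2 and 0.8. QIDS means "8.2; 7.6; 7.5; 6.9; 7.2 (common SD, 5.9") against "7.2; 6.6; 5.5; 4.4; 4.2, resulting in a mean difference of 3 points at the final study time point"; correlations 0.7 and 0.6. Heterogeneity rates 0.45 vs 1.2 (prenatal) and 1.15 vs 1.2 (postpartum), half of each arm in each stratum.

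**1. Head count**
- Approached to randomized: 374 × 0.80 × 0.77 = 230.4. This reproduces 230. In reverse, 230 / 0.616 = 373.4, rounded up to 374.
- Randomized to analyzable: 230 × 0.85 = 195.5, or 97.75 per arm. This does not reproduce 200.
- Number needed for 200: 200 / 0.85 = 235.3, so 236.
- 200 × 1.15 = 230 exactly. The match suggests that 15% was added to the target instead of dividing the target by 0.85. That is an inference, since the plan shows no formula. Refusal and eligibility, in the same sentence, are applied as fractions retained.
- Attrition at which 230 yields 200: 1 − 200/230 = 13.0%.

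**2. The plan's power figures at 100 per arm**
- Poisson, Wald test on the log rate ratio: ln(1.2/0.8) = 0.4055; SE = √(1/120 + 1/80) = 0.1443; 0.4055/0.1443 − 1.96 = 0.849; power 80.2% (plan: 80%).
- Heterogeneity, Wald test on the difference in log rate ratios with 50 per arm per stratum: |ln(0.45/1.2) − ln(1.15/1.2)| = 0.938; SE = √[(1/50)(1/0.45 + 2/1.2 + 1/1.15)] = 0.3085; power 86.0% (plan: 86%).
- Trajectory. The documents do not name the test, so I assume a 4-df group-by-time F test with equal correlation at the five listed time points. The differences 1, 1, 2, 2.5, 3 have mean 1.9 and squared deviations summing to 3.20. The noncentrality is (n/2) × 3.20 / [5.9² × (1 − ρ)] = 15.3 for ρ = 0.7 and 11.5 for ρ = 0.6. Power is 89.6% and 78.0% (plan: 89% and 77%).

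The stated figures are therefore sound for the sample size to which they refer.

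**3. The same formulas at 97.75 per arm, with dropouts contributing nothing**

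| Calculation | Plan | Recomputed, 100 per arm | Recomputed, 97.75 per arm |
|---|---|---|---|
| Poisson rate | 80% | 80.2% | 79.3% |
| Trajectory, ρ = 0.7 | 89% | 89.6% | 88.9% |
| Trajectory, ρ = 0.6 | 77% | 78.0% | 76.9% |
| Heterogeneity | 86% | 86.0% | 85.2% |

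The Poisson rate detectable with 80% power moves from 0.801 to 0.797, still a reduction of about 33% from 1.2.

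**4. If dropouts contribute part of their follow-up**

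With 15% of 115 lost (17.25 per arm), and each dropout supplying a fraction f of her assessments, the effective number per arm is 115 × (0.85 + 0.15f). The fraction is my assumption; the documents give no timing of attrition.
- f = 0: 97.75 per arm, Poisson power 79.3%.
- f = 0.25: 102.1 per arm, 81.0%.
- f = 0.50: 106.4 per arm, 82.6%.
- Break-even with 100 per arm: (100 − 97.75)/17.25 = 13% of assessments, which is less than one of the six visits.

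**The case against.** The strongest reply is that the loss of power may not occur at all. Attrition is described as happening during the study, outcomes are assessed every two months (section 9, Follow-Up Procedures), and section 12.3 plans an intention-to-treat analysis with rate regression and GEE or mixed models, all of which can use incomplete follow-up. On average, less than one assessment per dropout would restore the information of 100 complete women per arm. This stands as far as power is concerned. It does not repair the head count: section 12.2 does not say that partial follow-up is counted towards the 200.

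A second reply is that the gap is trivial. In size it is: 4.5 women, and falls in power of 0.7 to 1.1 points. Section 12.2 calls its power adequate with one scenario at 77%, so a Poisson figure of 79.3% would not overturn its conclusion.

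A reader might go further and infer that every power figure in section 12.2 is overstated. The documents do not support that. Each figure is stated for 100 per arm and reproduces there. Even at 97.75 per arm, the recomputed trajectory figures round to the 89% and 77% that the plan gives.

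**Conclusion.** The inconsistency is certain: with the plan's own 15% attrition, 230 randomized women leave 195.5, not 200. It is a minor error in a figure that the trial relies on, not evidence that the trial is underpowered.

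The consequence for power is conditional. If dropouts contribute nothing, the Poisson figure falls to about 79.3% and the heterogeneity figure to about 85.2%, each about one point below what is stated. If they contribute some follow-up, the loss shrinks or disappears. The trajectory result also rests on the assumed test and equal correlation. That calculation runs slightly above the plan's figures at 100 per arm, so the agreement after rounding should not be pressed beyond a point or so.

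**What to change.** Correct the closing paragraph of section 12.2 in one of two ways:
- State that about 195 women (97 to 98 per arm) are expected to be analyzable at 15% attrition, with Poisson power of about 79% and heterogeneity power of about 85% if dropouts contribute no data.
- Or state that partial follow-up from women who drop out is counted, say how much is expected, and give the power on that basis.

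The attrition assumption should not be lowered to 13% merely to fit 230: the plan bases its 15% on the team's own current data. If the sponsor wants 200 women left after 15% attrition, the consistent numbers are 236 randomized and, at the stated refusal and eligibility, about 384 approached (236 / 0.616 = 383.1). The size of the shortfall does not require that.

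The cost is a sentence or two and slightly lower stated power. No extra participants and no change to the design are needed.

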12.3 Statistical Methods

Data Analysis Plan. We will report our results according to CONSORT guidelines. Because our aim is also for dissemination and implementation, we will analyze our data according to the RE-AIM (Reach, Effectiveness, Adoption, Implementation, Maintenance) framework, which addresses both internal and external validity.

- 1) **Reach.** We will record the number of mothers approached, screened, eligible, and refusing participation; compare demographics of those refusing to those participating; record subject attrition; and note all adverse events. We will compare baseline characteristics across comparators.
- 2) **Effectiveness.** We will conduct an intention-to-treat analysis to compare differences between comparators for all primary and secondary outcomes.

a) Main Effects. Our main effects analysis answers the question: **Which strategy is more effective at improving outcomes among a screened population of pregnant and postpartum women with depressive symptoms?**

- Patient Reported Outcomes: To assess depressive symptoms, we will employ Poisson or negative binomial regression techniques to compare incident rates of symptomatic episodes (QIDS ≥ 11) over 12 months of follow-up. We will use generalized estimating equations or mixed linear models to examine group-by-time effects on mean depressive symptom scores – as well as on mean scores of each of our other measures – as a function of intervention arm.

- Engagement and retention in care: Depending on the frequency of the observed outcomes, we will employ logistic or binomial regression techniques to compare the proportion of participants who meet the definition of engagement, retention, or receipt of evidence-based care. Among those engaging with care, we will employ Poisson or negative binomial regression techniques (depending on data dispersion) to compare number of mental health visits attended. We will compare treatment choices across groups. If data distribution assumptions are not met, we will consider nonparametric procedures or transformation of data. We will assess clustering by enrollment site and intervention practitioner, and if necessary use generalized mixed models to account for these effects. If randomization fails to produce balanced groups, we will add to our models potentially confounding variables, for which distributions are unequal across groups.

b) Heterogeneity of Treatment Effect (HTE). The primary goal of our HTE analysis is to determine whether there is differential impact across our comparators, according to timing of screening (pregnancy vs. postpartum). Our hypothesis-driven HTE analysis thus answers the question: **When is the optimal time to deploy each comparator?** We will also explore HTE according to whether our participants have experienced violent trauma.

- Timing of Screening. The most likely HTE scenario is that Engagement-Focused Care Coordination will compare less favorably during pregnancy, when women are averse to medication treatment, and apt to misinterpret a referral to outside treatment as a road leading for pharmacotherapy.

- Trauma. In our own studies, we've documented a possible differential impact of PSE according to trauma history; however, because these data were not generated in the context of a comparative effectiveness trial, we consider our HTE-by-trauma analysis to be exploratory.

For both HTE analyses, we will use Rothman's methodology, evaluating moderation with stratified analyses (according to categorical predictors), followed by formal interaction term testing in our models. We will analyze repeated symptom measures as time-dependent covariates, and test them for interaction relative to concurrent outcomes. Within each subgroup, we will present treatment effect estimates and 95% confidence intervals.

3) **Adoption**. We will collect data related to the characteristics of the prenatal and pediatric clinics that may influence adoption (including size of staff, number of families served), and assess through qualitative techniques the potential for adoption of the intervention in these clinical venues.

4) **Implementation**. This is the subject of a separate IRB application.

5) **Maintenance**. Within the purview of this study, we will be unable to assess maintenance on the institutional level; however, at the individual level, our follow-up period will span 12 months.

13 Ethics/Protection of Human Subjects

This study is to be conducted according to applicable US federal regulations and institutional policies (which are based in federal regulations, guidance, and ICH Good Clinical Practice guidelines).

